### Design:

A BBAVF is a reliable autogenous hemodialysis access in patients without suitable cephalic vein.[1, 2] It can be created in either one or two stages.[3] The advantage of the one-stage approach is a shorter time between access creation and the cannulation for HD. The disadvantage is the potential for a longer upper arm incision if the AVF fails to mature. Although the two-stage approach can circumvent a more extensive procedure if the AVF fails, the need for two separate operations usually leads to more extended CVC dependency and a higher risk of CVC-related bacteremia (CRB). While literature confirms good results for BBAVFs, comparative studies of one-stage and two-stage methods are limited.[1] They rest on small case series and few have reported relevant clinical outcomes, including functional patency, duration of CVC dependency, and postoperative complications. In addition, an insufficient number of studies have used intention-to-treat analysis to account for the risk of primary fistula failure. The majority of these studies have concentrated on the fistula-related outcomes rather than patient centric and patient-reported outcomes (PROs), including the quality of life (QOL) measure.[3] There is a clinical equipoise in the surgical approach for the creation of a BBAVF and it is unclear whether patients prefer a one-stage or two-stage procedure.[1] Currently, the decision to use one-stage or two-stage approach varies widely among access surgeons and is based on factors such as the size of basilic vein and surgeon's bias or preference. A patient-centered approach, incorporating a balance between population-based evidence and individual patient perspectives might be preferred. This pilot study will allow us to understand patient-centered outcomes and QOL measures regarding the respective BBAVF techniques. We will use the valuable results to design a Patient-Centered Outcomes Research Institute (PCORI)-sponsored pragmatic clinical trial to determine the optimal surgical procedure for a BBAVF and to understand the perspective of patients receiving a complex AVF.

The plan is to enroll 10 patients (n=5 in each group) with ESRD receiving hemodialysis with a CVC from the Banner University Medical Center. Within each cohort, the subjects will be randomized in a 1:1 ratio to one. Within each cohort, the subjects will be randomized in a 1:1 ratio to one stage and two-stage surgical approaches. The randomization scheme is as follow:

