**Methods:**

The target population are patients on renal replacement therapy who are receiving hemodialysis (HD) with central venous catheters (CVCs) at the time of the surgery and are candidates for a new BBAVF. The surgery is a standard of care procedure that is being done whether the potential subject is enrolled in the study. Upon enrollment the study subject will fill out the PROMIS/CAT questionnaires. The study team will follow a randomized protocol so the study subject will be randomized to the one or two stage approach. The subjects will then be seen at the standard of care intervals for follow-up. At the 6 month and 12-month standard of care follow-up visits the subjects will be asked to fill out the PROMIS/CAT questionnaires again. The subjects medical record will be followed for AE and SAE study related problems during the 12 months post surgical procedure.

Primary endpoint is Primary Clinical Functional Patency, defined as the successful use of the index fistula with two dialysis needles for at least 75% of dialysis sessions within a 4-week period to achieve the prescribed dialysis. The primary endpoint will be compared between two techniques during available follow-up up to 12-months (from the index procedure in the one-stage approach and the first procedure for the two-stage approach). Secondary endpoints will include: 1) Fistula-related outcome: stenosis and thrombosis, wound infection, arm swelling, hand ischemia, and surgery or intervention; 2) CVC-related outcome: duration of catheter-dependency, infection, bacteremia, and additional CVC procedure (exchange, placement of new catheter); and 3) Composite outcomes of Primary Clinical Functional Patency or CVC-related bacteremia or death. We will compare the PROs using the Patient-Reported Outcome Measurement Information System (PROMIS) Computerized Adaptive Testing (CAT) in the randomized patients.

Hypothesis: Primary Clinical Functional Patency will be superior following two-stage approach compared with the one-stage BBAVF approach. Patients who underwent the two-stage procedure will have higher risks of infectious complications due to a more extended CVC dependency. The PROs will be affected by the number of procedures (one vs. two), postoperative fistula-related or CVC-related complications, and the duration of CVC dependency.

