**Statistical Analysis Plan:**

The primary analysis of the primary endpoint will be a comparison of the primary clinical functional patency by treatment approach, where the distributions are based on available follow up to 12 months. A log-rank test will be used to evaluate the null. The secondary analytic method of the secondary endpoints will utilize a Cox regression model to adjust for the subject factors to adjust for baseline imbalance such as vein size. Based on a recent publication utilizing primary patency rate as the main outcome, the reported rates of primary functional patency of one-stage BBAVF was 56% at 12-month follow-up and was 72% for the two-stage procedure.[12] Based on a two-sided Fisher's exact test at significance level of 5%, a sample size of 153 per group is required to achieve a power of 80% to detect the percentage patency difference of 16% (56% vs. 72%). A sample size of 336 participants (168 per arm), with an estimated loss to follow-up rate of 10%, will be required to achieve a 5% significance level. With the restraint of the time and resources of this ASDIN research grant, the pilot trial will be exploratory and will be used to demonstrate the feasibility of the research plan in a high-risk ESRD population and the recruitment target.

The changes in the individuals' PROMIS domain scores and overall scores from the baseline will be compared between the patients who underwent a one-stage procedure and those who had a two-stage procedure. The analysis will be performed after excluding those who do not complete the two-stage procedure (only first procedure for two-stage approach). The impact of clinical events including infection and catheter-related complication on PROMIS domain scores will be evaluated using the student T-test.

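### The only PROMIS comparison by technique drops two-stage patients who had just the first operation, so once anyone is dropped it no longer compares the randomised arms

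*Combined protocol and SAP*

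**What the plan says.** The PROMIS paragraph of the Statistical Analysis Plan specifies one comparison by technique. Changes from baseline are to be "compared between the patients who underwent a one-stage procedure and those who had a two-stage procedure". The next sentence restricts the set: "The analysis will be performed after excluding those who do not complete the two-stage procedure (only first procedure for two-stage approach"). The only other PROMIS analysis is a t-test of the effect of clinical events on scores, which does not compare techniques.

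Three other statements bear on this:

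- The Methods section describes the patient-reported comparison as using "Computerized Adaptive Testing (CAT) in the randomized patients", with no exclusion mentioned. It also says that at 6 and 12 months "the subjects will be asked to fill out the PROMIS/CAT questionnaires again".
- The Design section criticises earlier work because "an insufficient number of studies have used intention-to-treat analysis to account for the risk of primary fistula failure".
- The Design section gives as an advantage of staging that "the two-stage approach can circumvent a more extensive procedure if the AVF fails". Stopping after the first operation is therefore a foreseen course within the two-stage strategy.

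**The concern.** Whether the second operation takes place is settled after randomisation, and only the two-stage arm has a second operation to miss. On the plan's own account, fistula failure is one reason for stopping early. The rule can therefore remove early failures from the two-stage arm, while one-stage patients whose fistula fails stay in. From the first exclusion onward the groups are no longer those that randomisation made comparable. The plan neither names the result a completers analysis nor sets an as-randomised one beside it.

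The Design section states the purpose at stake: "This pilot study will allow us to understand patient-centered outcomes and QOL measures regarding the respective BBAVF techniques". It adds that the results will be used to design a larger trial. As written, the two-stage PROMIS result would describe only patients who had both operations. Yet the chance of stopping after stage one, and what that is like for the patient, is part of being assigned to two stages.

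**Working it through.** The plan gives no figure for the PROMIS comparison, so there is none to reproduce. Its sample size for a future trial (153 per group for 56% against 72%) does reproduce, with exact Fisher power of 80.3%, but it does not bear on this point.

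**1. Who is in the comparison**

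| Course of the patient | One-stage arm | Two-stage arm |
|---|---|---|
| Fistula fails early, no further stage | included | excluded |
| Assigned surgery completed, fistula fails later | included | included |
| Assigned surgery completed, fistula works | included | included |

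The asymmetry is confined to the first row.

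**2. Size of the shift**

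Let f be the share of the two-stage arm excluded, mC the mean PROMIS change in completers, mN the mean change in non-completers, and d = mC − mN, scored so that higher is better.

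- As-randomised two-stage mean: (1 − f)·mC + f·mN
- Mean under the exclusion rule: mC
- Shift: mC − [(1 − f)·mC + f·mN] = f·d

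This holds whatever happens in the one-stage arm and whatever the true effect. A simulation with 2,000,000 patients per arm and a true completer effect of 2 points agreed: shifts of +0.5, +1.0 and +2.0 points for d = 5, and the same with a minus sign for d = −5, at f = 10%, 20% and 40%.

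**3. Inputs**

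- From the plan: 5 patients per arm, and "the reported rates of primary functional patency of one-stage BBAVF was 56% at 12-month follow-up and was 72% for the two-stage procedure".
- Assumed, because the documents do not give them: f; a gap of 3 to 5 points in absolute value; an SD of change of 5 to 10 points.

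The patency rates imply 5 × (1 − 0.56) = 2.2 one-stage and 5 × (1 − 0.72) = 1.4 two-stage patients without primary functional patency at 12 months. These are not estimates of exclusions. The rule can remove only those two-stage failures that occur before stage two. Supposing that half or all of the 28% fail that early gives f = 14% or 28%, which is a further assumption.

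**4. Results**

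| f | Shift, gap 3 | Shift, gap 5 | Chance that at least 1 of 5 is excluded, 1 − (1 − f)^5 |
|---|---|---|---|
| 10% | 0.30 | 0.50 | 41% |
| 14% | 0.42 | 0.70 | 53% |
| 20% | 0.60 | 1.00 | 67% |
| 28% | 0.84 | 1.40 | 81% |
| 40% | 1.20 | 2.00 | 92% |

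**5. Against the pilot's sampling error**

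- One excluded (5 against 4, f = 20%): SE = SD × √(1/5 + 1/4) = 3.35 for SD 5, or 6.71 for SD 10. A shift of 0.6–1.0 points is 0.6/6.71 = 0.09 to 1.0/3.35 = 0.30 SE.
- Two excluded (5 against 3, f = 40%): SE = SD × √(1/5 + 1/3) = 3.65 or 7.30. A shift of 1.2–2.0 points is 1.2/7.30 = 0.16 to 2.0/3.65 = 0.55 SE.

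**6. If the rule were carried into the larger trial**

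A second simulation assumed no true arm difference, failures equally common in both arms (10–28%), failures scoring 5–10 points worse, and SD 10. Removing failures from the two-stage arm only gave false-positive rates of about 5–6% at 5 per arm, but 7–60% at 168 per arm. With all randomised patients analysed, the rate stayed near 5%.

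**The case against.** The best defence is that the rule answers a question the plan asks. The Methods section hypothesises that patient-reported outcomes depend on whether a patient has one operation or two, and grouping by operations received fits that. This is a reason to keep the comparison, but not to make it the only one. It is also an imperfect answer to that question, since removing early failures from one group mixes the number of operations with having a fistula good enough to proceed.

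Second, failing to complete treatment is not the same as fistula failure. A one-stage patient whose fistula fails has still had the assigned operation, and a one-stage patient never operated on would also drop out of a comparison by procedure undergone. Stage two may be missed for reasons other than failure. All of this is fair. It limits what can be said about the direction of the shift, but the condition of reaching a second operation still falls on one arm only.

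Third, the exclusion is openly stated, the intention-to-treat remark in the Design section concerns fistula failure rather than quality of life, and the Methods wording about randomised patients may reflect an as-randomised intention. These points stand in part. But that wording specifies no analysis set, and the only analysis that is specified excludes patients.

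Fourth, the pilot is declared exploratory, the numerical effect is well inside the noise, and the questionnaires would exist for later use. The first two are accepted. As to the third, a result that can be produced later if someone thinks to do so is not a planned result.

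**Conclusion.** The concern holds, and it is limited to the PROMIS analysis. The one specified comparison by technique conditions on a post-randomisation event that exists in one arm, carries no label saying so, and has no as-randomised analysis beside it. If every two-stage patient reaches the second operation and all are treated as assigned, the problem does not arise.

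The size and direction of any distortion cannot be determined from the documents. Under the assumed ranges it is at most 2.0 points and about half a standard error, so it would not by itself drive a conclusion in ten patients. The substantive harm is that the two-stage arm's patient-reported evidence leaves out those who stop early, each of whom is 20% of a five-patient arm. The plan should be corrected before analysis, particularly because the pilot is meant to inform a larger trial in which the same rule could matter much more.

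**What to change.** Replace the exclusion sentence in the Statistical Analysis Plan with wording such as:

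> PROMIS changes will be compared by randomised arm in all randomised patients with available follow-up scores, whether or not the second stage was performed; missing questionnaires and deaths will be reported by arm.

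Keep the comparison restricted to two-stage completers as a sensitivity analysis, labelled as such. Reconcile the Methods section and the Statistical Analysis Plan so that both name the same population for patient-reported outcomes.

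The cost is wording only. The 6- and 12-month questionnaires are already planned for all subjects, so no visit or instrument is added. One limitation remains: non-completers may not return questionnaires, and having a follow-up score is itself a post-randomisation condition. Reporting missing questionnaires and deaths by arm makes that visible but does not remove it.

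### The unadjusted t-test of PROMIS scores by clinical event mixes the event with the randomised arm on the plan's own hypotheses, so it does not estimate the impact of events

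*Combined protocol and SAP*

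**What the plan says.** The last sentence of the Statistical Analysis Plan is the whole specification of this analysis: "The impact of clinical events including infection and catheter-related complication on PROMIS domain scores will be evaluated using the student T-test". It gives no covariates, visit, event window, or choice between score and change.

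The hypothesis paragraph in Methods makes two statements that bear on it. On event risk: "Patients who underwent the two-stage procedure will have higher risks of infectious complications due to a more extended CVC dependency". On quality of life: "The PROs will be affected by the number of procedures (one vs. two), postoperative fistula-related or CVC-related complications, and the duration of CVC dependency".

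On data collection, Methods says "Upon enrollment the study subject will fill out the PROMIS/CAT questionnaires" and "At the 6 month and 12-month standard of care follow-up visits the subjects will be asked to fill out the PROMIS/CAT questionnaires again". Events are followed throughout the year: "The subjects medical record will be followed for AE and SAE study related problems during the 12 months post surgical procedure".

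Two other sentences might seem to supply what is missing, but neither does. The change-from-baseline sentence ("The changes in the individuals' PROMIS domain scores and overall scores from the baseline will be compared") concerns the comparison of one-stage with two-stage patients. The Cox model with adjustment for baseline imbalance is assigned to the secondary endpoints and is not stated for PROMIS.

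**The concern.** The stated aim is causal: how much an infection or catheter complication changes quality of life. A two-group t-test answers that only if patients with and without events are otherwise comparable, and the plan gives reasons to think they are not. It expects arm to influence who has an event and, separately, to influence the PROMIS score. Arm is then a common cause of grouping and outcome, and the unadjusted difference contains an arm component even if events do nothing. Baseline health is a further likely confounder of any such grouping, although the documents give no data on it.

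The Design section says the results will be used to design a larger pragmatic trial and to understand patient-centred outcomes. A difference reported as an impact could be carried into that work when part or all of it belongs to the surgical approach.

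**Working it through.** **Inputs from the documents.** 10 patients, 5 per arm (Design). PROMIS at enrolment, 6 and 12 months; events over 12 months (Methods). The plan gives no figure for this analysis to reproduce. Its only sample-size calculation concerns patency. Event rates, PROMIS SD, arm effect and baseline correlation are not given, so the values below are assumptions. The true event effect is set to zero throughout.

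**Arm component.** Let p1 and p2 be the event risks in the one-stage and two-stage arms (equal allocation) and A the arm effect on PROMIS that does not pass through the event.
- Two-stage share among patients with an event: p2/(p1+p2).
- Two-stage share among patients without: (1−p2)/(2−p1−p2).
- Spurious event effect: A × (difference of the two shares).

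| p1 v p2 | Share, event | Share, no event | Difference | A=3 | A=5 | A=10 |
|---|---|---|---|---|---|---|
| 10% v 30% | 0.750 | 0.438 | 0.312 | 0.9 | 1.6 | 3.1 |
| 20% v 40% | 0.667 | 0.429 | 0.238 | 0.7 | 1.2 | 2.4 |
| 20% v 60% | 0.750 | 0.333 | 0.417 | 1.3 | 2.1 | 4.2 |
| 10% v 50% | 0.833 | 0.357 | 0.476 | 1.4 | 2.4 | 4.8 |

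The component is zero if p1 = p2 or A = 0. The plan's hypotheses expect neither.

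**Baseline component (general, not documented here).** Let D be the baseline gap between event and non-event patients and rho the baseline/follow-up correlation, with equal SDs. The spurious effect is rho × D on raw scores and (rho−1) × D on change scores.
- D = 5, rho = 0.5: 2.5 raw, −2.5 change.
- D = 5, rho = 0.7: 3.5 raw, −1.5 change.
- If event odds double per SD of worse baseline, with SD 10, rho = 0.6 and about 31% having events, D is about −6.3. That gives 0.6 × −6.3 = −3.8 raw and −0.4 × −6.3 = +2.5 change.

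The sign depends on the choice between score and change, which the plan does not make.

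**Timing.** An event after month 6 cannot have affected the month-6 score. Whether such a patient would count as an event case at month 6 is not stated.

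**Precision at N = 10.**
- t-test, 3 events v 7 without, SD 10: half-width of the 95% CI = 2.306 × 10 × √(1/3 + 1/7) = 15.9 points.
- Linear model with event, arm and baseline: 10 − 4 = 6 residual df, against 8 for the t-test. In simulated 10-patient trials under the baseline assumptions above, with or without a 5-point arm effect, this model brings the bias to about zero. Its root-mean-square error is about 7.3 points, against 7.6 to 8.6 for the raw-score t-test and 6.4 to 6.5 for the change-score t-test. Its half-width is about 16 points.
- Probability that the event or non-event group has fewer than 2 patients, binomial with n = 10: 74%, 38% and 15% at event risks of 10%, 20% and 30%.

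**The case against.** The strongest reply is that this is a minor exploratory analysis in a 10-patient feasibility pilot. No stated decision depends on it, and an interval of about 16 points either side swamps biases of one to four points. Adjustment does not make the result informative. All of that stands, and it limits how much weight the point should carry. It does not rescue the method: a specific test is named for a causal quantity that it does not estimate under the plan's own hypotheses, and the covariates needed are already collected.

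A reader might also infer that the plan counts events occurring after a questionnaire, or treats the 6- and 12-month scores of one patient as independent. Neither is written. A single test at 12 months, after a year of event follow-up, would largely avoid both. These are gaps in specification, not demonstrated faults.

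Nor do the documents support saying that the estimate is biased by a known amount or in a known direction, or that frailer patients are known to have more events. Only the arm route rests on their text.

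Finally, adjusting for arm and baseline does not finish the job. Methods names catheter duration as the reason for the higher infection risk and, separately, as a driver of patient-reported outcomes, so some confounding remains.

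**Conclusion.** The concern holds in limited form. The unadjusted comparison is confounded by arm if the plan's hypotheses are true, so it cannot be read as the impact of infection or catheter complications on PROMIS. Under the assumed event risks, a 5-point arm effect produces about 1.2 to 2.1 points of spurious effect in the first three scenarios and 2.4 in the widest (10% v 50%). The actual size and direction cannot be derived from the documents. The missing visit, score and event window should be specified. At this sample size imprecision is at least as serious as bias, so the gain is a correctly defined and correctly labelled estimate, not a conclusive one.

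**What to change.** Replace the t-test in the Statistical Analysis Plan with a linear model (ANCOVA), fitted for each PROMIS domain at one stated visit. The terms are an indicator for an event before that questionnaire, randomised arm, and the baseline score of the same domain. Also:
- Report the event coefficient with its 95% CI as an exploratory association, not an impact, and note that residual confounding by catheter duration remains.
- Show event and non-event scores by arm, next to the baseline scores.
- If fewer than 2 patients fall in either event group, report descriptively only.
- State whether the exclusion of patients who do not complete the two-stage procedure applies to this analysis. The text leaves this unclear, and applying it would add selection.
- Keep the repeated-measures model with a time-updated event indicator for the larger trial. With at most 20 follow-up scores from 10 patients it would be fragile here.

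The cost is SAP wording and a little analysis work, with no new visits or data, because PROMIS scores and events are already collected. The statistical price is two degrees of freedom (6 residual instead of 8), and the interval remains wide.
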